7.1.3. Dosing (Day 1)

The following assessments and procedures will be performed and documented at this visit:

- Vital signs. Prior to dosing, blood pressure, heart rate, respiratory rate and temperature will be measured. For all other time points, only blood pressure and heart rate will be measured
- Randomization to treatment
- Administration of study drug. Dose will be administered orally with 240 mL of room temperature water in an upright position under fasting conditions at approximately 8 am. Subjects should not drink water and need to maintain an upright position for 2 hours after the administration of the study drug. Lunch will be served at approximately 4 hours after the administration and dinner as the standard meal at approximately 10 hours post dose. If needed, evening snack can be provided. Time of administration will be documented for both study drug and meals.
- Pharmacokinetic blood samples will be collected at the following time points: Pre-dose (within 30 min prior) and at 1, 2, 3, 4, 5, 6, 7, 8, 9, 10, 11, 12, 14, 16, 24, 36, 48, 72, 96, 120, 144, and 168 hours after dosing (acceptable windows: ± 2 min for 0 to 2-hr post dose period and ± 5 min thereafter)
- Assessment of AEs and concomitant medications.

All doses of study drug will be administered orally under fasting conditions at approximately 8 am on the day of dosing. Subjects will be closely supervised and within sight of study personnel within 8 hours after dosing. Actual times for dosing, each assessment and meals (start times for meals on the day of dosing) must be recorded. Any deviations from the protocol-specified administration schedule will also be documented.

7.1.4. Days 2 through 7

The following assessments and procedures will be performed and documented.

- Daily vital sign measurements
- Pharmacokinetic blood sample collections (acceptable windows: ± 5 min). See PK timepoints in section 7.1.3 and footnote of Table 5-1
- Assessment of AEs and concomitant medications daily
- Discharge from CRU on Day 3 after the 48-hour after dosing PK sample is obtained. Subjects will be remined to return to CRU at defined time to provide PK sample and to receive study assessments

7.1.5. Day 8

The following assessments and procedures will be performed and documented.

- Physical examination
- Vital sign measurements

- A single 12-lead ECG
- Overnight fasting blood sample collection for safety tests
- Drug and alcohol test
- Pharmacokinetic blood sample collections (acceptable windows: ± 5 min). See PK timepoints in section 7.1.3 and footnote of Table 5-1
- Assessment of AEs and concomitant medications daily

7.2. Part 1- Period Two

After a wash-out period for at least 14-day since the last dosing, subjects will be evaluated for their eligibility for Period Two. Eligible subjects will crossover to the alternative reference or test drug. Thus, subjects who receive levamlodipine treatment in Period One will now receive NORVASC® treatment in Period Two, while subjects who receive NORVASC® treatment in Period One will now receive levamlodipine treatment in Period Two. The same procedure will be performed at the same time points as noted for Period One.

7.2.1. Admission (Day 0)

The following assessments and procedures will be performed and documented:

- Admission to CRU
- Cross-over to treatment
- Physical examination
- Vital signs
- A single 12-lead ECG record
- Overnight fasting blood sample collection for safety tests
- Drug/alcohol test
- Urine pregnant test for females of childbearing potential
- Assessment of AEs and concomitant medications.

7.2.2. Dosing (Day 1)

The following assessments and procedures will be performed and documented:

- Vital signs. Prior to dosing, blood pressure, heart rate, respiratory rate and temperature will be measured. For all other time points, only blood pressure and heart rate will be measured
- Administration of study drug. Dose will be administered orally with 240 mL of room temperature water in an upright position under fasting conditions at approximately 8 am. Subjects should not drink water and need to maintain an upright position for 2 hours after the administration of the study drug. Lunch will be served at approximately 4 hours after the administration and dinner as the standard meal at approximately 10 hours post dose. If needed, evening snack can be provided. Time of administration will be documented for both study drug and meals.
- Pharmacokinetic blood samples will be collected at the following time points:

Pre-dose (within 30 min prior) and at 1, 2, 3, 4, 5, 6, 7, 8, 9, 10, 11, 12, 14, 16, 24, 36, 48, 72, 96, 120, 144, and 168 hours after dosing (acceptable windows: ± 2 min for 0 to 2-hr post dose period and ± 5 min thereafter)

• Assessment of AEs and concomitant medications.

All doses of study drug will be administered orally under fasting conditions at approximately 8 am on the day of dosing. Subjects will be closely supervised and within sight of study personnel within 8 hours after dosing. Actual times for dosing, each assessment and meals (start times for meals on the day of dosing) must be recorded. Any deviations from the protocol-specified administration schedule will also be documented.

7.2.3. Days 2 through 7

The following assessments and procedures will be performed and documented.

- Daily vital sign measurements
- Pharmacokinetic blood sample collections (acceptable windows: ± 5 min). See PK timepoints in section 7.2.2 and footnote of Table 5-2
- Assessment of AEs and concomitant medication daily
- Discharge from CRU on Day 3 after the 48-hour after dosing PK sample is obtained. Subjects will be remined to return to CRU at defined time to provide PK sample and to receive study assessments

7.2.4. Day 8

The following assessments and procedures will be performed and documented.

- Physical examination
- Vital sign measurements
- A single 12-lead ECG
- Overnight fasting blood sample collection for safety tests
- Drug/alcohol test
- Urine pregnancy test for females of childbearing potential
- Pharmacokinetic blood sample collections (acceptable windows: ± 5 min). See PK timepoints in section 7.2.2 and footnote of Table 5-2
- Assessment of AEs and concomitant medication daily
- Discharge from the CRU

7.3. Part 2 (Food Effect)

7.3.1. Admission (Day 0)

Subjects who have completed Part 1 will be rolled over to Part 2 after a wash-out period for at least 14-days since the last dosing to assess food effect on the PK profile of levamlodipine maleate tablets from CSPC. Eligible subjects will be admitted to the CRU on Day 0 and remain sequestered at the CRU until the collection of the 48-hour PK sample after dosing.

On arrival at the clinical research unit, all subjects will undergo the following assessments:

- Physical examination
- Vital signs including blood pressure, heart rate, respiratory rate and temperature
- A single 12-lead ECG
- Overnight fasting blood sample collection for safety tests
- Drug/alcohol test
- Urine pregnancy test for females of childbearing potential
- Admission to the CRU
- Assessment of AEs and concomitant medications

Enrolled patients will be fasted from 10 pm the day prior to dosing until approximately 4 hours after administration the next day (dosing day). Water intake will be permitted until 6 am of the dosing day.

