Clinical safety tests		Х								Х
Drug/alcohol test		Х								Х
Pregnancy test ²		Х								Х
Dose administration			Х							
PK blood samples ³			Х	Х	Х	Х	Х	Х	Х	Х
AE & ConMed		Х	Х	Х	Х	Х	Х	Х	Х	Х
Discharge from CRU					Х					

Table 5-2. Schedule of Procedures for Part 1 - Period 2

¹ Complete vital sign measurements at 0, 24, 96 and 168 hours after dosing. Blood pressure and heart rate only at other time points. Three measurements of blood pressure at screening visit and a single measurement at other time points.

² Urine test for females of childbearing potential only.

³ Pharmacokinetic blood samples will be collected at the following time points: Pre-dose (within 30 min prior) and at 1, 2, 3, 4, 5, 6, 7, 8, 9, 10, 11, 12, 14, 16, 24,

36, 48, 72, 96, 120, 144, and 168 hours after dosing (acceptable windows: $\pm 2 \min$ for 0 to 2-hr post dose period and $\pm 5 \min$ thereafter)

AE = adverse event; ConMed = concomitant medications; CRU = clinical research unit; ECG = electrocardiogram; PK = pharmacokinetics.

	Wash-out	Clin	Clinical Research Unit (CRU)				h Unit (CRU) Clinical Visits			
Day	At least 14 days since the last dosing	Day 0 (Admission)	Day 1 (Dosing)	Day 2	Day 3	Day 4	Day 5	Day 6	Day 7	Day 8 ⁵
Admission to CRU		Х								
Physical examination		Х								Х
Vital signs ¹		Х	Х	Х	Х	Х	Х	Х	Х	Х
12-lead ECG		Х								Х
Clinical safety tests		Х								Х
Drug/alcohol test		Х								Х
Pregnancy test ²		Х								Х
High-fat/calorie meal ³			X							
Dose administration			X							
PK blood samples ⁴			X	Х	Х	X	Х	Х	Х	Х
AE & ConMed		X	X	Х	X	X	Х	Х	X	X
Discharge from CRU					X					

 Table 5-3.
 Schedule of Procedures for Part 2 (Food Effect)

¹ Complete vital sign measurements on Day 0 and 0, 24, 96 and 168 hours after dosing. Blood pressure and heart rate only at other time points.

² Urine test for females of childbearing potential only.

³ The meal should be started 30 minutes prior to administration of study drug, and finished in 30 minutes or less

⁴ Pharmacokinetic blood samples will be collected at the following time points: Pre-dose (within 30 min prior) and at 1, 2, 3, 4, 5, 6, 7, 8, 9, 10, 11, 12, 14, 16, 24,

36, 48, 72, 96, 120, 144, and 168 hours after dosing (acceptable windows: $\pm 2 \min$ for 0 to 2-hr post dose period and $\pm 5 \min$ thereafter)

⁵ End-of the study or early termination.

AE = adverse event; Con Med = concomitant medications; CRU = clinical research unit; ECG = electrocardiogram; PK = pharmacokinetics.

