7.3.2. Dosing (Day 1)

The following assessments and procedures will be performed and documented at this visit:

- Vital signs. Prior to dosing, blood pressure, heart rate, respiratory rate and temperature will be measured. For all other time points, only blood pressure and heart rate will be measured
- High-fat/high-calorie meal. Following an overnight fast of at least 10 hours, subjects should start the recommended meal 30 minutes prior to administration of the drug product. Study subjects should eat the a high-fat / high-calorie meal in 30 minutes or less. This meal should derive approximately 150, 250 and 500-600 calories from protein, carbohydrate and fat, respectively. Subjects should receive standardized meals scheduled at the same time in each period of the study.
- Administration of study drug. Dose will be administered orally with 240 mL of room temperature water in an upright position under using meal conditions at approximately 8 am. No food should be allowed for at least 4 hours post-dose. Water can be allowed as desired except for one hour before and after drug administration. Subjects should receive standardized meals scheduled at the same time in each period of the study.
- Pharmacokinetic blood samples will be collected at the following time points: Pre-dose (within 30 min prior) and at 1, 2, 3, 4, 5, 6, 7, 8, 9, 10, 11, 12, 14, 16, 24, 36, 48, 72, 96, 120, 144, and 168 hours after dosing (acceptable windows: ± 2 min for 0 to 2-hr post dose period and ± 5 min thereafter)
- Assessment of AEs and concomitant medications.

Subjects will be supervised and within sight of study personnel within 8 hours after dosing. Actual times for dosing, each assessment and meals (start times for meals on the day of dosing) must be recorded. Any deviations from the protocol-specified administration schedule will also be documented.

7.3.3. Days 2 through 7

The following assessments and procedures will be performed and documented.

- Daily vital sign measurements
- Pharmacokinetic blood sample collections (acceptable windows: ± 5 min). See PK timepoints in section 7.3.2 and footnote of Table 5-3
- Assessment of AEs and concomitant medications daily
- Discharge from CRU on Day 3 after the 48-hour after dosing PK sample is obtained. Subjects will be remined to return to CRU at defined time to provide PK sample and to receive study assessments

7.3.4. Day 8

The following assessments and procedures will be performed and documented.

- Physical examination

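### The Part 2 admission section orders a fast that runs through dosing, which contradicts the pre-dose high-fat meal required in the rest of the protocol

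*Protocol*

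**What the plan says.** Protocol 7.3 is headed as the food-effect part. Its admission section, 7.3.1, says: "Enrolled patients will be fasted from 10 pm the day prior to dosing until approximately 4 hours after administration the next day (dosing day". The same sentence, word for word, stands in 7.1.2, where it governs the fasted Part 1. Section 7.3.1 adds: "Water intake will be permitted until 6 am of the dosing day".

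The dosing section, 7.3.2, says: "Following an overnight fast of at least 10 hours, subjects should start the recommended meal 30 minutes prior to administration of the drug product". It places the dose "in an upright position under using meal conditions at approximately 8 am". On water it says: "Water can be allowed as desired except for one hour before and after drug administration". After the dose: "No food should be allowed for at least 4 hours post-dose".

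The footnote to Table 5-3 in section 5.2 agrees with 7.3.2: "The meal should be started 30 minutes prior to administration of study drug, and finished in 30 minutes or less". The synopsis, the text of 5.2 and section 5.4 give the same meal timing. Sections 5.1 and 8.2 and SAP 1.2 also describe the Part 2 dose as taken with a high-fat, high-calorie meal.

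Objective 2 (Protocol section 4) is the food effect. Protocol 12.3 bases it on changes in log-transformed AUC and Cmax of (S)amlodipine between fasting and fed conditions.

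**The concern.** The admission section is what staff follow on the evening the fast begins. Taken literally, it allows no food before the dose or for about 4 hours after it, so the Part 2 dose would be given fasted. The sections covering the next morning require a meal before the dose.

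Part 2 is single-arm and has no concurrent fasted group. The food effect rests on comparing each subject's Part 2 profile with that subject's fasted levamlodipine profile from Part 1. A subject dosed under 7.3.1 would contribute fasted data on both sides of that comparison and pull the fed/fasted ratio toward 1, that is, toward no food effect.

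The documents contain no rule on which section governs. SAP 1.2 only describes the meal, SAP section 1 defers PK analysis to a separate plan, and SAP section 7 lists only the randomization wording as a change from the protocol.

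**Working it through.** The plan states no figure to reproduce. The check sets the instructions side by side and applies clock arithmetic.

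**Inputs**
- Fast starts at 10 pm and ends about 4 h after the dose (7.3.1).
- Dose at about 8 am (7.3.2).
- Meal starts 30 min before the dose and takes at most 30 min (7.3.2, 5.2, Table 5-3).
- Fast before the meal: at least 10 h in 7.3.2, approximately 10 h in the synopsis and 5.2.
- Water: stops at 6 am (7.3.1); barred for 1 h either side of the dose (7.3.2).
- Target of 27 Part 1 completers, who roll over to Part 2 (5.3).

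**Step 1: food before the dose.** Under 7.3.1 the fast runs from 22:00 to 08:00 + 4 h = 12:00, a total of 14 h. Under 7.3.2 the meal starts at 08:00 − 0:30 = 07:30 and is over by 08:00, wholly inside that fast. The conflict does not depend on the exact clock time: the meal always precedes the dose, and the fast always extends past it.

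**Step 2: food after the dose.** About 4 h in 7.3.1 and at least 4 h in 7.3.2. These agree, so the conflict is confined to the pre-dose period.

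**Step 3: effect on the food-effect estimate.** Let δ be the true mean log fed/fasted ratio and f the fraction of Part 2 subjects dosed fasted. A subject dosed fasted twice has an expected log ratio of 0, if period effects are set aside and the food effect is assumed similar across subjects. Then

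E(estimate) = (1 − f)·δ + f·0 = (1 − f)·δ.

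At f = 0 the estimate is unaffected. At f = 1 the expected log ratio is 0 and the ratio is 1. One subject in 27 gives f = 1/27 = 0.037 and a factor of 1 − 0.037 = 0.963. The documents give no value for f, so this shows direction and cost per subject, not an expected bias.

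**Step 4: fast length.** 22:00 to 07:30 is 9.5 h, which is 0.5 h short of the 7.3.2 minimum if dosing is at exactly 8:00. It fits the looser wording of 5.2. With the meal at 8:00 and the dose at 8:30, the fast is 10 h.

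**Step 5: pre-dose water.** Under 7.3.2 the last water is at 08:00 − 1 h = 07:00; under 7.3.1 it is at 06:00. The difference is 1 h.

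**The case against.** The strongest reply is that the fed condition is not in doubt. The meal appears in the synopsis, 5.1, 5.2, Table 5-3 (with its own row and footnote), 5.4, 7.3.2, 8.2 and SAP 1.2. One sentence, apparently carried over from 7.1.2, stands against at least eight statements. A careful site would probably serve the meal. Section 7.3.2 also requires meal start times and deviations to be recorded, and SAP Listing 16.2.6.3 covers the pre-dose meal, so an omitted meal should be visible. All of this stands. It makes silent contamination unlikely, but it does not remove the contradictory instruction.

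A reader might go further in four ways that the documents do not support.
- *That the 10 pm start and the 10-hour fast cannot both be met.* The dose time is approximate, and Step 4 shows a timetable that meets both.
- *That the two Part 2 water rules are incompatible.* The rule in 7.3.2 is permissive, so stopping at 6 am breaches neither.
- *That every Part 2 subject is affected.* Every subject is covered by the inconsistent wording, but that is not the same as being dosed fasted.
- *That Parts 1 and 2 must share one set of water and posture rules.* For the Part 1 dose, 7.1.3 says: "Subjects should not drink water and need to maintain an upright position for 2 hours after the administration of the study drug". Part 2 has a 1-hour water restriction and, though dosing is upright, states no upright period afterwards. These rules belong to different parts and do not contradict each other. The documents show no PK consequence, and Part 2 always follows Part 1, so fed status is already confounded with period. Common rules would be a design preference.

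**Conclusion.** The point holds as a conflict between site instructions. Section 7.3.1 cannot be followed together with the synopsis, 5.2, Table 5-3, 5.4 and 7.3.2. Neither the SAP nor any precedence rule settles it. It needs correcting because, if followed literally, it would defeat the fed condition behind one of the two study objectives.

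The size is conditional. Each subject dosed fasted, out of 27, would take about 3.7% off the expected log fed/fasted ratio. This assumes 27 subjects enter Part 2, a similar food effect across subjects and no period effect. How many subjects would be handled that way is unknown, and the clear intent elsewhere suggests few or none. The half-hour shortfall in the fast and the 1-hour difference in the water cut-off are minor wording matters. That the sentence was carried over from 7.1.2 is an inference from the identical text.

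**What to change.** Reconcile 7.3.1 with the synopsis, 5.2, Table 5-3, 5.4 and 7.3.2, so that a single food instruction governs the Part 2 dose from the evening before until the post-dose restriction ends. In the same edit, align the fast start, the meal and dose times and the two statements of fast length (7.3.2 against the synopsis and 5.2), and state one pre-dose water cut-off for Part 2. Which times and restrictions to keep is for the sponsor and investigator.

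The cost is protocol wording only, handled as an amendment under section 18 and best settled before any Part 2 dosing. It adds no subjects, visits or assays.

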7.3.2. Dosing (Day 1)

The following assessments and procedures will be performed and documented at this visit:

- Vital signs. Prior to dosing, blood pressure, heart rate, respiratory rate and temperature will be measured. For all other time points, only blood pressure and heart rate will be measured
- High-fat/high-calorie meal. Following an overnight fast of at least 10 hours, subjects should start the recommended meal 30 minutes prior to administration of the drug product. Study subjects should eat the a high-fat / high-calorie meal in 30 minutes or less. This meal should derive approximately 150, 250 and 500-600 calories from protein, carbohydrate and fat, respectively. Subjects should receive standardized meals scheduled at the same time in each period of the study.
- Administration of study drug. Dose will be administered orally with 240 mL of room temperature water in an upright position under using meal conditions at approximately 8 am. No food should be allowed for at least 4 hours post-dose. Water can be allowed as desired except for one hour before and after drug administration. Subjects should receive standardized meals scheduled at the same time in each period of the study.
- Pharmacokinetic blood samples will be collected at the following time points: Pre-dose (within 30 min prior) and at 1, 2, 3, 4, 5, 6, 7, 8, 9, 10, 11, 12, 14, 16, 24, 36, 48, 72, 96, 120, 144, and 168 hours after dosing (acceptable windows: ± 2 min for 0 to 2-hr post dose period and ± 5 min thereafter)
- Assessment of AEs and concomitant medications.

Subjects will be supervised and within sight of study personnel within 8 hours after dosing. Actual times for dosing, each assessment and meals (start times for meals on the day of dosing) must be recorded. Any deviations from the protocol-specified administration schedule will also be documented.

7.3.3. Days 2 through 7

The following assessments and procedures will be performed and documented.

- Daily vital sign measurements
- Pharmacokinetic blood sample collections (acceptable windows: ± 5 min). See PK timepoints in section 7.3.2 and footnote of Table 5-3
- Assessment of AEs and concomitant medications daily
- Discharge from CRU on Day 3 after the 48-hour after dosing PK sample is obtained. Subjects will be remined to return to CRU at defined time to provide PK sample and to receive study assessments

7.3.4. Day 8

The following assessments and procedures will be performed and documented.

- Physical examination
- Vital sign measurements
- A single 12-lead ECG
- Overnight fasting blood sample collection for safety tests
- Drug/alcohol test
- Urine pregnant test for females of childbearing potential
- Pharmacokinetic blood sample collections (acceptable windows: ± 5 min). See PK timepoints in section 7.3.2 and footnote of Table 5-3
- Assessment of AEs and concomitant medications daily

7.4. Early Withdrawal Visit

In the event that a subject discontinues study participation at any time prior to the final End-of-Study visit, if possible, the subject should complete all follow-up assessments, as described for Day 8. The reason for discontinuation must be fully documented in the subject's source documentation and in the CRF.

8. TREATMENT OF SUBJECTS

8.1. Methods of Assigning Subjects in Part 1

Subject treatment assignment will be based on a generated randomization scheme with a ratio of 1:1 (test: reference). Each treatment group will have 16 subjects randomized to receive either test drug or reference drug.

8.2 Methods of Assigning Subjects in Part 2

All subjects who have completed Part 1 will be rolled over to Part 2 after a wash-out period for at least 14 days since the last dosing to assess food effect on the PK profile of levamlodipine maleate tablets. Subjects will receive a single oral administration of study drug under a high-fat /

high-calorie meal. This meal should derive approximately 150, 250 and 500-600 calories from protein, carbohydrate and fat, respectively.

